## 6.3 Sample repository

Samples will be prepared, aliquoted, and stored as below:

- Serum – draw 5 mL in red- or tiger-topped tube or equivalent. Aliquot into four 0.6 mL capped tubes and freeze at -80°C.
- Plasma, citrated – draw 10 mL into two 5 mL in blue-topped tubes. After processing, aliquot plasma into eight 0.6 mL capped tubes and freeze at -80°C.
- Plasma lithium heparin – draw 10 mL into two 5 ml green-topped tubes.
- Packed Cells – packed cells remaining from citrated plasma, aliquoted into two 2.0 mL capped tubes for later batched shipment. Samples are to be frozen at -80°C.

Samples may be initially stored at -20°C in a non-frost-free freezer for a maximum of 30 days. Repository samples will be labeled with a repository ID number and will carry no direct identifiers of the subject. The sample repository will be maintained indefinitely.

## 7. ADVERSE EVENT CRITERIA AND REPORTING

We will use the descriptive terminology developed by the National Cancer Institute for reporting adverse events (AEs): Common Toxicology Criteria for Adverse Events (CTC) version 4. 0 dated May 28 2009. The CTC includes a grading (severity) scale for each adverse event term. Grades were developed using the following guidelines:

- Grade 0 - No adverse event or within normal limits
- Grade 1 - Mild adverse event
- Grade 2 - Moderate adverse event
- Grade 3 - Severe adverse event
- Grade 4 - Life threatening or disabling adverse event
- Grade 5 - Death related to adverse event

In general, investigators are to report adverse events as diseases or syndromes whenever possible, instead of reporting individual component symptoms, signs, laboratory abnormalities, and sequel. The following types of occurrences are not considered adverse events and do not need to be reported: 1) pre-existing medical conditions that are present at the start of the study; and 2) previously scheduled hospitalizations and hospitalizations needed for diagnostic or elective surgical procedures for the management of pre-existing medical conditions.

### 7.1 Expectedness of Adverse Events

#### 7.1.1 Criteria for Expectedness

Each AE should be evaluated by the site investigator as to whether it was expected or unexpected. An unexpected AE is defined as any AE the nature, severity, or frequency of which is not consistent with either:

- 1) the known or foreseeable risk of AEs associated with the procedures involved in the research that are described in the IRB-approved study protocol, any applicable investigator brochure, the current IRB-approved informed consent document, or other relevant sources of information such as product labeling or package inserts; or
- 2) the expected natural progression of any underlying disease, disorder, or condition of the subject and his/her predisposing risk factor profile for the AE.

AEs that do not meet the above criteria for an unexpected AE should be graded as expected.

#### 7.1.2 Toxicities associated with rituximab

##### Non-Infectious pulmonary toxicity

Non-infectious pulmonary toxicity is a rare but potentially fatal complication of rituximab therapy (Hadjinicolaou et al, 2012). A total of 121 cases of potential rituximab-induced lung toxicity were identified from 61 clinical studies and case reports. In most cases, rituximab was part of combination chemotherapy for treatment of cancers. The mean time of onset from the last rituximab infusion until symptom development is 30 days (range 0-158 days). Most patients with this side effect improved completely with corticosteroids. The disease was fatal in 18 cases.

The following Adverse Events and other safety information are described in the Rituxan® Package Insert (2011).

##### Severe Infusion Reactions

Rituximab can cause severe, including fatal, infusion reactions. These severe reactions typically occurred during the first infusion with time to onset of 30 to 120 minutes. Monitor closely during infusion; discontinue with grade 3 or 4 infusion reactions. Signs and symptoms of

severe infusion reactions may include urticaria, hypotension, angioedema, hypoxia, or bronchospasm, and may require interruption of rituximab administration. The most severe manifestations and sequelae include pulmonary infiltrates, acute respiratory distress syndrome, myocardial infarction, ventricular fibrillation, cardiogenic shock, and anaphylactic and anaphylactoid events. In the reported cases, the following factors were more frequently associated with fatal outcomes: female gender, pulmonary infiltrates, and chronic lymphocytic leukemia or mantle cell lymphoma.

### **Hypersensitivity reactions**

Rituximab has been associated with hypersensitivity reactions (non-IgE-mediated reactions), which may respond to adjustments in the infusion rate and in medical management. Hypotension, bronchospasm, and angioedema have occurred in association with rituximab infusion (see Severe Infusion Reactions). Therefore, subjects require close monitoring during first and all subsequent infusions. Premedication with diphenhydramine and acetaminophen is recommended.

Rituximab infusion will be interrupted for severe hypersensitivity reactions and can be resumed at a 50% reduction in rate (e. g., from 100 mg/hour to 50 mg/hour) when symptoms have completely resolved. Treatment of these symptoms with diphenhydramine and acetaminophen is recommended; additional treatment with bronchodilators or IV saline may be indicated. In most cases, patients who have experienced non-life-threatening hypersensitivity reactions have been able to complete the full course of therapy. Medications for the treatment of hypersensitivity reactions, e. g., epinephrine, antihistamines, and glucocorticoids, should be available for immediate use in the event of a reaction during administration.

### **Other infusion reactions**

Other reported adverse events, including fever, chills, headache, nausea, vomiting, rhinitis, and mild hypotension, occurred primarily during rituximab infusions and typically responded to an interruption of the infusion and resumption at a slower rate. More rare but serious events include tumor lysis Syndromes (in subjects with malignant lymphoma and chronic lymphocytic leukemia), mucocutaneous reactions, cardiac arrhythmias and angina in subjects with preexisting cardiac disease, and renal failure (also associated with tumor lysis).

### **Infections**

Serious including fatal, bacterial fungal and new or reactivated viral infections can occur during and up to one year following the completion of rituximab – based therapy .New or reactivated viral infectious included cytomegalovirus, herpes simplex virus, parvovirus B19, varicella zoster virus, West Nile virus and hepatitis B and C. Discontinue rituximab for serious infections and institute appropriate ant -infective therapy.

### **Cardiovascular Reactions**

Infusions should be discontinued in the event of serious or life-threatening cardiac arrhythmias. Patients who develop clinically significant arrhythmias should undergo cardiac monitoring during and after subsequent infusions of rituximab. Patients with pre-existing cardiac conditions including angina have had recurrences of these events during rituximab therapy and should be monitored throughout the infusion and immediate post-infusion period.

### **Renal**

Rituximab administration has been associated with severe renal toxicity, including acute renal failure requiring dialysis, and in some cases has led to a fatal outcome in subjects treated for lymphoma who have tumor lysis syndrome, often associated with concomitant cisplatin therapy.

### **Severe mucocutaneous reactions**

Mucocutaneous reactions, some with fatal outcome, have been reported in subjects treated with rituximab. These reports include paraneoplastic pemphigus (an uncommon disorder which is a manifestation of the subject's underlying malignancy), Stevens-Johnson syndrome, lichenoid dermatitis, vesiculobullous dermatitis, and toxic epidermal necrolysis. The onset of the reaction in the reported cases has varied from 1-13 weeks following rituximab exposure. Subjects experiencing a severe mucocutaneous reaction will not receive any further infusions and will receive prompt medical evaluation. Skin biopsy may help to distinguish among different mucocutaneous reactions and guide subsequent treatment. The safety of re-administration of rituximab to subjects with any of these mucocutaneous reactions has not been determined.

### **Hematologic events**

In clinical trials, Grade 3 and 4 cytopenias were reported in 48% of subjects treated with rituximab; these include: lymphopenia (40%), neutropenia (6%), leukopenia (4%), anemia (3%), and thrombocytopenia (2%). The median duration of lymphopenia was 14 days (range, 1 to 588 days) and of neutropenia was 13 days (range, 2 to 116 days). A single occurrence of transient aplastic anemia (pure red cell aplasia) and two occurrences of hemolytic anemia following rituximab therapy were reported.

In addition, there have been a limited number of post-marketing reports of prolonged pancytopenia, marrow hypoplasia, and late onset neutropenia (defined as occurring 40 days after the last dose of rituximab) in subjects with hematologic malignancies. In reported cases of late onset neutropenia (NCI-CTCAE Grade 3 and 4), the median duration of neutropenia was 10 days (range 3 to 148 days). Documented resolution of the neutropenia was described in approximately half of the reported cases; of those with documented recovery, approximately half received growth factor support. In the remaining cases, information on resolution was not provided. More than half of the reported cases of delayed onset neutropenia occurred in subjects who had undergone prior autologous bone marrow transplantation. In an adequately designed, controlled, clinical trial, the reported incidence of NCI-CTCAE Grade 3 and 4 neutropenia was higher in subjects receiving rituximab in combination with fludarabine as compared to those receiving fludarabine alone (76% [39/51] vs. 39% [21/53]).

### **Carcinogenesis, mutagenesis, and impairment of fertility**

No long-term animal studies have been performed to establish the carcinogenic or mutagenic potential of rituximab, or to determine its effects on fertility in males or females. Male and female subjects will be advised to use effective contraceptive methods during treatment and for 12 months following rituximab therapy.

### **Hepatitis B Reactivation with Related Fulminant Hepatitis and Other Viral Infections**

Hepatitis B virus (HBV) reactivation with fulminant hepatitis, hepatic failure, and death has been reported in some subjects with hematologic malignancies treated with rituximab. The majority of subjects received rituximab in combination with chemotherapy. The median time to the diagnosis of hepatitis was approximately 4 months after the initiation of rituximab and approximately one month after the last dose. A direct causal relationship between rituximab and HBV viral reactivation has not been established.

The following additional serious viral infections, either new, reactivated or exacerbated, have been identified in clinical studies or post-marketing reports. The majority of patients received Rituxan in combination with chemotherapy or as part of a hematopoietic stem cell transplant. These viral infections included JC virus [progressive multifocal leukoencephalopathy (PML)], cytomegalovirus, herpes simplex virus, parvovirus B19, varicella zoster virus, West Nile virus,

and hepatitis C. In some cases, the viral infections occurred up to one year following discontinuation of Rituxan and have resulted in death.

### **Vaccinations**

The safety of immunization with live viral vaccines following rituximab therapy has not been studied and vaccination with live virus vaccines is not recommended. The ability to generate a primary or anamnestic humoral response to vaccination is currently being studied. If vaccination using non-live vaccines is being considered, physicians should consult the Centers for Disease Control and Prevention (CDC) guidelines.

### **Post Marketing Experience**

Because these reactions are reported voluntarily from a population of uncertain size, it is not always possible to reliably estimate their frequency or establish a causal relationship to drug exposure. Decisions to include these reactions in labeling are typically based on one or more of the following factors: (1) seriousness of the reaction, (2) frequency of reporting, or (3) strength of causal connection to rituximab.

*Hematologic:* prolonged pancytopenia, marrow hypoplasia, and late onset neutropenia, hyperviscosity syndrome in Waldenstrom's macroglobulinemia.

*Cardiac:* fatal cardiac failure.

*Immune/Autoimmune Events:* uveitis, optic neuritis, systemic vasculitis, pleuritis, lupus-like syndrome, serum sickness, polyarticular arthritis and vasculitis with rash.

*Infection:* increased in fatal infections in HIV-associated lymphoma.

*Skin:* severe mucocutaneous reactions.

*Gastrointestinal:* bowel obstruction and perforation.

#### **7.1.3 Toxicities associated with plasma exchange**

Subjects undergoing plasma exchange may experience the following side effects/complications:

- Complications secondary to vascular access including: hematoma, venous sclerosis, thrombosis and embolism, inadvertent arterial puncture, pneumothorax and/or hemothorax
- Vasovagal reaction
- Citrate toxicity including: circumoral paresthesias, nausea, vomiting, chills, muscular twitching, tetany, and syncope. Severe citrate toxicity may manifest as cardiac arrhythmia.
- Transfusion reaction associated with plasma, including: fever, chills, urticaria,
- Transfusion-related acute lung injury (TRALI)

#### **7.1.4 Toxicities associated with corticosteroids**

The following adverse side effects may be seen in subjects on steroid therapy:

- Cardiovascular: arrhythmia, edema, hypertension
- Central nervous system: insomnia, delirium, psychoses, and seizures
- Dermatologic: hirsutism, skin atrophy, bruising, hyperpigmentation
- Endocrine and metabolic: glucose intolerance, Cushing's syndrome, pituitary adrenal axis suppression (adrenal insufficiency)

- Hematologic: transient leukocytosis
- Ocular: cataracts, glaucoma
- Miscellaneous: infections, hypersensitivity reactions, buffalo hump, moon face

## 7.2 Relatedness to Participation in the Research Study

Each AE should be evaluated as to whether it was related or possibly related to participation in the research study (meaning that there is a reasonable possibility that the AE may have been caused by the procedures involved in the research). AEs determined to be solely caused by an underlying disease, disorder, or condition of the subject; or other circumstances unrelated to the research should be categorized as being not related to participation in the research.

## 7.3 Relatedness to Use of the Study Drug (Rituximab)

Each AE should also be evaluated as to whether it was related to the use of rituximab:

Definite	An AE is clearly related to use of rituximab
Probable	An AE has a strong temporal relationship to use of rituximab, and another etiology is significantly less likely.
Possible	An AE has a strong temporal relationship to use of rituximab, and an alternative etiology is equally or less likely.
Unlikely	An AE has little or no temporal relationship to use of rituximab, and/or a more likely alternative etiology exists.
Not Related	An AE is not related to use of rituximab (no temporal relationship, or a much more likely alternative etiology exists).

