## DEFINITIONS

**Day 1:** The first day a subject receives plasma exchange for treatment of TTP.

**Treatment Response:** 2 consecutive days with platelet count  $\geq 150,000/\mu\text{L}$

**Durable Treatment Response:** Treatment Response that persists for  $\geq 30$  days after discontinuation of plasma exchange.

**Exacerbation:** Recurring TTP  $\leq 30$  days after a Treatment Response and discontinuation of plasma exchange.

[figure not shown]
**Refractory TTP:** Failure to achieve a Treatment Response by day 28, or failure to achieve a Durable Treatment Response by day 60.

**Composite Primary Endpoint:** Exacerbation or Refractory TTP.

**Relapse:** Recurring TTP  $> 30$  days after Treatment Response.

**Observation Period:** The interval of 2 years after a subject first achieves a Durable Treatment Response.

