### 1.2 Secondary Endpoints

#### 1.2.1 Clinical and Safety Endpoints

- Incidence of Durable Treatment Response
- Number of days to Durable Treatment Response
- Number of plasma exchanges to Durable Treatment Response
- Incidence of relapse
- Numbers of days to relapse
- 4 week, 1 year and 2 year incidence of death
- Incidence, type and severity of treatment-related adverse events

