## **2.4. Proposed Study of Low-Dose Adjuvant Rituximab for TTP**

The substitution of low dose for standard dose rituximab would reduce the drug cost 7-fold to approximately \$2,000 for a 4 week course, which approximates the cost of one plasma exchange procedure. Low dose rituximab (100 mg) may also have a decreased risk of complications. Two studies of low dose rituximab for ITP reported mainly mild infusional reactions. The rate of serious complications is probably low but not known precisely: one of 59 patients with ITP treated with low dose rituximab developed interstitial pneumonia that responded to steroids (Provan 2007, Zaja 2010).

Based on the currently available data we propose a pilot study to determine whether adjuvant low dose rituximab, in addition to standard therapy with plasma exchange and corticosteroids, can shorten the time to treatment response and reduce the risk of exacerbation for patients with TTP caused by ADAMTS 13 deficiency.

We will use a novel assay to evaluate the utility of ADAMTS 13 as a biomarker to assess the response to therapy and predict the risk of relapse. If successful this therapy would not only improve patient outcomes but also would be cost saving compared to standard dose, salvage rituximab, which is the current standard of care.

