### **5.1.2 Administration**

Each study site will utilize its own supply of rituximab, and will store under conditions consistent with the drug's package insert. The prescribed dose of rituximab will be reconstituted in normal saline to a concentration no more than 4 mg/mL. Rituximab dose is fixed dose of 100 mg, given intravenously, repeated at one-week intervals for a total of four doses. Rituximab is to be administered only by slow intravenous infusion; it is not to be administered as an IV push or bolus. The infusion may be administered via a peripheral venous catheter; no central catheter is required. Treatment may be on an out-patient basis; in-patient hospitalization is not required. Each rituximab infusion bag will be labeled by the pharmacy as "Investigational Drug – ART Study". An Investigational Drug Accountability Log will be provided to each site by the sponsor-investigator and will be maintained by personnel at each study site. This Log will be updated by study personnel each time rituximab is dispensed by the pharmacy and a copy will be provided to the site research coordinator and the Washington University liaison. All expired or unused drug will be destroyed in accordance with local institutional practice.

Rituximab is to be infused every 7 days with a window of 5-9 days considered acceptable. If a dose is administered outside the 5-9 day window, then the schedule will be altered such that the next dose will be given 7 days later and any subsequent doses will be given at 7 day intervals.

The first rituximab infusion will be given as soon as possible after study eligibility is established but before the 5th plasma exchange.

The initial rituximab solution for infusion will be administered intravenously at an initial rate of 50 mg/hr. Subsequent rituximab infusion can be administered at an initial rate of 100 mg/hr.

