### 5.2.5 Treatment of Refractory TTP

The subject will be considered to have Refractory TTP if they do not have a Treatment Response by day 28, or do not have a Durable Treatment Response by day 60. The treatment of Refractory TTP will include resuming plasma exchange and corticosteroids. Additional salvage therapy is at the physician's discretion and can include full dose rituximab  $375 \text{ mg/m}^2$  weekly for 4 doses. Patient with Refractory TTP will be followed for 2 years with laboratory monitoring.

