## 7.4 Reporting and Monitoring Adverse Events

Information about all adverse events that occur within 1 year after enrollment in subjects will be collected. The clinical course of AEs will be followed until a medical outcome is determined. Additional information that becomes available may be added to previously submitted AE reports at any time. Site investigators should follow their local IRB's guidelines in terms of reporting AEs to them. All AEs must be reported to Washington University's Clinical Coordinating Center (CCC) on designated case report forms (CRFs) to be provided by the sponsor-investigator.

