### 7.4.1 Expedited Reporting of Serious Adverse Events

Serious adverse events (SAEs) are defined as AEs that cause death, a life-threatening adverse experience, or a persistent or significant disability/incapacity (i.e. Grade 4 and 5 events); inpatient hospitalization or prolongation of existing hospitalization; pregnancy abortion, or a congenital anomaly, birth defect, or cancer in a neonate/infant born to a female subject.

Serious adverse events must be reported by Clinical Center personnel to the Washington University CCC within 24 hours of the Clinical Center's awareness (Monday-Friday) by electronically mailing the completed Serious Adverse Event form and de-identified source documentation to [name] ([[contact]](mailto:[contact])) and [name], BSN ([[contact]](mailto:[contact])). Each Clinical Center will follow their local IRB reporting policy of AEs and SAEs. If a SAE is determined to be unexpected and possibly, probably, or definitively related to rituximab or to participation in the research study, it must be reported to the local IRB within 24 hours of the Clinical Center's awareness of the event. Data on all serious adverse events that occur in subjects will be collected through the end of their study participation (i.e. the full 2-year follow-up period).

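### Relatedness is graded to rituximab at any dose, so events after full-dose salvage enter the treatment-related adverse event endpoint by default and may overstate low-dose toxicity

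*Combined protocol and SAP*

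**What the plan says.** Section 7.3 instructs: "Each AE should also be evaluated as to whether it was related to the use of rituximab". Its five grades, from definite to not related, depend on timing and on competing causes. None mentions which dose or which course of rituximab was given.

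The safety endpoint in section 1.2.1 is "Incidence, type and severity of treatment-related adverse events". The protocol does not define treatment-related or link it to section 7.3. Section 9.2 compares its incidence with historical controls by Fisher's exact test, and considers a chi-square test for type and severity. It neither censors nor separates events after salvage.

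The study regimen is given in section 5.1.2: "Rituximab dose is fixed dose of 100 mg, given intravenously, repeated at one-week intervals for a total of four doses". For refractory disease, section 5.2.5 adds: "Additional salvage therapy is at the physician's discretion and can include full dose rituximab", at 375 mg/m² weekly for four doses. Section 5.2.6 allows the same for relapse. Refractory TTP is defined as "Failure to achieve a Treatment Response by day 28, or failure to achieve a Durable Treatment Response by day 60".

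On collection, section 7.4 states: "Information about all adverse events that occur within 1 year after enrollment in subjects will be collected". Section 7.4.1 states: "Data on all serious adverse events that occur in subjects will be collected through the end of their study participation", which it specifies as the 2-year follow-up. Salvage ends protocol rituximab if the four doses are not complete (section 8.1), but it is not an off-study criterion (section 8.2).

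**The concern.** The trial is described as a pilot of safety and efficacy, and part of the argument for the dose in section 2.4 is safety: "Low dose rituximab (100 mg) may also have a decreased risk of complications". The same section concedes that the rate of serious complications at this dose is not precisely known. A reader will therefore take the treatment-related adverse event incidence as describing four doses of 100 mg.

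As written, an infusion reaction or infection after a full-dose course would be graded as related to rituximab, and nothing then keeps it out of that incidence. The mixing is selective, because full-dose salvage is named only for subjects whose disease is refractory or relapses. The apparent toxicity of the low dose would rise as its efficacy fell. With 20 subjects, one or two such cases visibly move the result.

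**Working it through.** **Dose contrast.** The protocol's own ratio is a cost ratio: about $14,000 for a standard course (section 2.3) against about $2,000 for the low-dose course (section 2.4). 14,000 / 2,000 = 7.0, which reproduces the stated 7-fold.

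The protocol gives no ratio in milligrams, so body surface area (BSA) must be assumed. Ratio = 375 × BSA / 100.

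| Assumed BSA (m²) | Full dose per infusion (mg) | Ratio to 100 mg |
|---|---|---|
| 1.6 | 600 | 6.0 |
| 1.87 | 701 | 7.0 |
| 2.2 | 825 | 8.25 |

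Both regimens have four doses, so the ratio per course is the same: 2,400 to 3,300 mg against 400 mg.

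**Does salvage fall inside the collection windows?** For a refractory subject, yes. If salvage starts on day 60, four weekly infusions end on day 60 + 21 = 81, leaving about 365 − 81 = 284 days of the 1-year window (treating enrollment as close to day 1).

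For relapse, mostly not for non-serious events. Section 2.2 cites a median time to relapse of 22 months in one review, no relapse in the first year in the French study, and late relapses at 9 months to 4 years. These figures come from earlier rituximab series. Relapses after year 1 can add serious events only.

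**How many subjects?** Inputs from section 9.1 are 20 enrolled and a planned composite rate of 10%.

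- Expected composite failures: 20 × 0.10 = 2. The chance of at least one is 1 − 0.90^20 = 0.88.
- This is an upper bound for the refractory route. The composite also includes exacerbation, for which section 5.2.3 names only plasma exchange and corticosteroids, and salvage is discretionary. An exacerbation can still become refractory under the day-60 limb of the definition, so the working range is 0 to 2 of 20.
- If the composite rate stayed at the historical 55%, the corresponding upper bound would be 20 × 0.55 = 11.

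**Effect on incidence.** Incidence counts subjects, so a subject adds 1/20 = 5 points only if no related event occurred before salvage. Let b be the true low-dose incidence, s the share salvaged and q the chance of a related event after salvage. Assuming independence:

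expected increment = (1 − b) × s × q

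Take s at its planned upper value of 0.10, with b and q assumed:

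| b | q = 0.2 | q = 0.5 | q = 1.0 |
|---|---|---|---|
| 0.10 | 1.8 points | 4.5 points | 9.0 points |
| 0.20 | 1.6 points | 4.0 points | 8.0 points |
| 0.30 | 1.4 points | 3.5 points | 7.0 points |

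For scale, the exact 95% interval is 1.2% to 31.7% for 2 of 20 and 3.2% to 37.9% for 3 of 20. The shift is systematic but smaller than the sampling uncertainty.

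**The case against.** **The text does not say that salvage events count.** The heading of section 7.3 refers to the study drug, section 5.1.2 fixes that drug at 100 mg and labels it investigational, and section 8.1 distinguishes protocol low-dose therapy from salvage. Section 7.2 also requires a separate judgement of relatedness to research procedures, under which discretionary salvage might be called unrelated. This stands in part: a reader might infer an explicit rule of inclusion, and there is none. But the grading text names rituximab without qualification and no other section excludes these events, so they are included by default.

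**Counting everything is a legitimate whole-strategy estimate.** This also stands, and that analysis should be kept. The protocol does not state it as the intent, however, and it cannot by itself support a statement about the toxicity of 100 mg.

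**Cutting at salvage could bias the comparison with controls.** This is correct. Section 2.4 calls salvage rituximab the current standard of care, so historical controls may have had it too. Cutting only the treated group would favour the study regimen.

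**The data already allow a split.** Medication logs continue through follow-up (sections 6.1.5 and 6.1.7, Tables 4 and 5), so a reader who infers that the trial cannot describe low-dose toxicity goes too far. What is missing is a planned split, which is stronger than one chosen after the events are known. The adverse event form itself is not in the documents, so it cannot be said to lack the field.

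**Conclusion.** The point holds as a gap in definition with a modest effect. Relatedness is not tied to dose, the endpoint's key term is undefined, and salvaged subjects stay under observation, so the low-dose incidence may be overstated. At the planned rate, 0 to 2 of 20 subjects would be exposed through refractory disease, plus any early relapses, at 5 points for each subject whose only related event follows salvage. This rests on the assumed BSA range for the dose contrast, on salvage being full-dose rituximab when given, and on the planned 10% rate. Exposure would be greater if efficacy were poorer.

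A reader might add all composite failures to all expected relapses and infer an inflation of 10 to 25 points. The documents do not support that figure. It needs every such subject to be salvaged with full-dose rituximab, to have a related event inside the window and to have had none before. It also counts late relapses and exacerbations for which no salvage rituximab is named. Nor is the direction of any bias against the historical controls known, because their own exposure to salvage rituximab is not described.

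The primary endpoint, sample size and safety reporting are unaffected. This is an inexpensive improvement worth making.

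**What to change.** 1. Leave all adverse event and serious adverse event collection, expedited reporting and the all-events comparison as they are.
2. Record on the adverse event form, or derive from infusion and medication-log dates, whether onset was before or after the first full-dose rituximab infusion.
3. In section 1.2.1, define treatment-related and say how it relates to the grades in section 7.3.
4. In section 9.2, report treatment-related events with onset before the first full-dose infusion as the low-dose safety estimate, and tabulate later events separately.
5. For any comparison with historical controls, apply the same cut at salvage rituximab in both groups, or use the all-events analysis.

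The cost is one field or derived variable and a few sentences. If the cut is used against controls, their salvage dates must be abstracted. Low-dose follow-up becomes shorter in salvaged subjects, so follow-up time should be shown beside the incidence. Late effects of the low dose cannot be cleanly assigned after salvage: section 7.1.2 cites lung toxicity at up to 158 days after the last infusion and infections at up to a year. Separate tables make that uncertainty visible but do not remove it.
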